- *Each study site to describe the source population and definition of the study cohort Each study site to specify the target groups for which influenza vaccination is recommended, which vaccines are used in the database catchment area, and how the choice of vaccine brand happens*

Study period

The study follow-up will start before the seasonal influenza vaccine is available and before the influenza virus circulation begins in the country/region, to ensure that all vaccinations and all outcomes in the defined cohort are captured. If only aggregated data will be collected that does not allow the shortening of the study subjects' follow-up as part of the statistical analysis, the follow-up may be restricted to the time the vaccine first becomes available or the virus circulation starts, whichever occurs first. The study period will finish at the end of the influenza season.

- *Each study site to specify the study period: the definition of the beginning and end of the study period*
- *Each study site to specify the early, middle and end of the influenza epidemic at the study site according to the information provided by the local influenza surveillance system.*

For the pooled analysis, a harmonised minimum period will be defined (e.g. from week 40 till week 20), but if needed, it will be extended to fully cover the vaccination campaign and the epidemic in each study site. Definition of shorter time periods (e.g. early, middle and end season) will be developed to take into account differences in influenza activity over time and probable development of immunity in unvaccinated population through encounters with the circulating viruses

For addressing the secondary objective of estimating influenza vaccine effectiveness over several seasons, multiple study periods will be combined. If possible, the information from the local surveillance systems of major circulating strains in the study regions will be considered in the analysis. The details of the analysis will be described in the generic study site level SAP.

Study population and follow-up

Cohort of interest

The study cohort comprises the characterised by place of residence, or catchment population of a health care service providing the relevant information for the analyses. The databases may also be characterised by or restricted to e.g. age, or medical, physiological or occupational conditions (e.g. pregnancy, health care workers, other risk/target groups).

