Potential confounders and effect modifiers

The following list presents known and potential confounders and effect modifiers in population-based IVE studies using secondary data from pre-existing databases (please also refer to DRIVE deliverable 4.1: Framework for analysis of influenza vaccine effectiveness studies).

The minimum set for a pooled analysis is marked with an asterisk (*). If available, also as many as possible of the other determinants will be harmonised between the study sites for pooled analysis according to the guidelines for harmonisation, developed according to availability of data and included in the generic study site level SAP.

- Age*
- Sex*
- Number of healthcare visits 12 months prior to the study period describing a study subject's healthcare seeking behaviour
 - (For children) Also adherence to the local childhood vaccination programme
- Chronic underlying conditions like chronic pulmonary disease, cardiovascular disease, metabolic disorders, renal disease, treatment-induced immunosuppression and disease-induced immunosuppression, medically attended obesity etc.

- (For children) Perinatal and congenital risk factors (e.g. birth weight and/or maturity at birth, perinatal factors, inborn errors of metabolism, relevant malformations and congenital syndromes)
- Number of hospitalisations 12 months prior to the study period to be used as proxy for the severity of the chronic conditions
- Pregnancy
- Influenza vaccination in previous influenza seasons; preferably more than one season,
- Pneumococcal vaccination
- Institutionalization, nursing home residence
- Contraindication to influenza vaccination
- Use of influenza antivirals
- Use of statins
- Socio-economic status or applicable proxy
- Smoking behaviour or parental smoking behaviour (for subjects ≤18 years)
- (For children) Number of siblings

➤ *Each study site to describe the factors included in the study & how these are identified.*

The list will be updated based on results of DRIVE D2.2: Systematic review of the sources of confounding, bias and strategies to manage their impact in influenza vaccine effectiveness studies, due June 2018.

Sources of information

The studies will utilize secondary data from existing population-based national, local or cohort based databases, health and social registers and/or surveillance systems by combining the information with an individual identification number, or relevant aggregation. . Examples of source databases:

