- *Each study site to specify the data checking and cleaning process*

Statistical analysis

This section describes the main principles for the study site level analysis. The statistical analyses are attempted to be harmonised between the study sites, to optimise the numbers of variables to be used in the adjustment and the heterogeneity/homogeneity between the study sites. After analysing the characteristics and structure of the databases used in participating study sites, a generic site level Statistical Analysis Plan (SAP) will be provided, including guidelines for harmonisation, with details/alternatives for defining the variables. The generic site level SAP will be updated annually, and attached as an Annex 2 to the generic protocols. Details on the site-specific analyses will be provided in the site-specific Statistical Analysis Plans (SAPs), attached as Annexes of the site-specific protocols. Information on the two-stage pooling of data from several study sites is provided in the DRIVE D4.4: “*Generic statistical analysis plan; combining information on influenza vaccine effectiveness across study sites.*” Based on the D4.4, season-specific SAPs for pooling data across study sites will be written. The season-specific SAP is expected to be modified each season to reflect the specificities of the season’s influenza epidemic as well as changes in participating study sites and data availability.

Individual follow-up

The follow-up of an individual belonging to the defined study cohort starts at a fixed time point at the start of the study period, and the follow-up continues until the first occurrence of the defined outcome, until another event leading to right-censoring as defined below, or until the end of the study period, whichever comes first.

Study subjects are right-censored, i.e. their individual follow-up ends, after the first occurrence of the outcome defined for the analysis in question. Other reasons for right-censoring have to be defined according to data availability and harmonised between the study sites: death, moving out of from the cohort catchment area, administration of an influenza vaccine of a type or brand other than the exposure defined for the analysis, having and influenza infection caused by an influenza virus type/subtype/lineage other than the one defined as the outcome for the analysis.

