The analysis must be conducted for each exposure and outcome of interest separately. Confounder-adjusted brand-specific, type specific or overall IVE estimates will be obtained from multivariable regression models, regressing the health outcomes of interest on exposure status, age, sex and the confounders of interest. In case of effect modifiers, an interaction term between exposure and the effect modifier will be included in the regression model or stratified regression analyses will be performed.

Depending on the type of data available, the analytical method(s) will be described in the generic study site level SAP and in a study-specific SAP before the start of the study period. For the outcome of interest, irrespective of its type, multivariable logistic regression will be used, if only the number of events as vaccinated and unvaccinated by number of subjects vaccinated and unvaccinated at the end of the follow-up is known. If the number of events by person time and vaccination status can be assessed, Poisson regression will be used. In case of time-to-event data, Cox regression (proportional hazards) will be used.

Missing data

The cohort should be defined so that the missing data is minimised: the cohort should cover all subjects targeted, especially for the vaccination, and only those subjects. Especially the outcome should be caught non-differentially, i.e. similarly for vaccinated and unvaccinated (see section Study population and follow-up; Cohort of interest). Missing data for events occurring during the follow-up is not available, since 'no record' means by definition 'no event' (unless also the negative

outcome information, e.g. negative influenza tests are available, when a nested case control analysis could be performed).

Missing data may be present, if historical data for background factors at start of the follow-up is not available, e.g. if the subject has moved into the attachment area of the database recently, or it is incomplete, e.g. only part of the databases used in defining the different background factors are available. This subcohort may be excluded from the adjusted analyses.

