Study sites may publish their own data independently from DRIVE. If DRIVE funds were used to collect the data, this should be acknowledged in the publications.

Authorship of joint DRIVE publications follows the rules of International Committee of Medical Journal Editors (ICMJE).

Logistical aspects

Study sites

A study site is any entity that administers and conducts the individual studies according to the regulations and ethical codes of EU and the country and institutions involved. The study site collects the data and provides it to DRIVE as a whole. EFPIA members do not have access to this data. Study sites may be local, regional or national; examples include GP and hospital networks having access to databases from established population based cohorts, influenza surveillance schemes and public health institutes utilizing routine health care, social service and demographic databases.

Study leader

In each study site, a study leader (principal investigator) will coordinate and be responsible for the study at the study site level and act as focal point towards DRIVE. The WP7 of DRIVE is in charge of the pooled and/or meta-analysis across several study sites.

- *Each study site to introduce the study leader and the study team with brief CVs and Declarations of Interest.*

Standard operating procedures and quality issues

Standard operating procedures (SOPs) developed and harmonised in DRIVE should be adapted to the individual studies and used by investigators during all the steps of the study for identification of study subjects, data collection, laboratory methods, data entry, monitoring, etc. as provided in DRIVE. Guidelines of definitions for the study variables will be included in the generic study site level analysis plan (SAP), for harmonisation of the methods between the study sites (Annex 2).

Potential systematic or major deviations from the SOP and generic study site level SAP should be described for further development of the methodology and for interpretation of the results. DRIVE WP 2 and WP 3 will further evaluate the quality of the studies and develop guidelines and methods for improving the quality.

- *Each study site to adapt DRIVE study SOPs and guidelines to be used by the study team and provide a summary of systematic or other major deviations from them to WP7, to be stored*

Training

- *Each study site to describe the trainings to be organised*

Changes to the protocol

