Annex 1: The dataset

Annex 1 defines the data elements to be used for estimating brand-specific VE in a population based cohort study using secondary data from pre-existing databases. The minimum dataset is marked with an asterisk(*), but preferably the most important covariates to adjust for will be included. According to these data elements, the analysis database will be developed to include the defined outcome events by person months vaccinated, (partially vaccinated) and unvaccinated, considering the events leading to right-censoring, and the covariates needed for adjustment or stratification.

The database may alternatively be structured for aggregated data, initially based on these data elements.

Instructions for harmonisation of the variables and the structure of analysis database will be provided in the generic study site level Statistical Analysis Plan (SAP), Annex 2. Season-specific updates in Annex 2 will be implemented to Annex 1, if needed.

DRIVE – The dataset for estimating VE in a population based cohort study using secondary data from pre-existing databases. The minimum data set is marked with an asterisk(*)�.

	Variable	Description	Format	Values and coding	Example
General	idcountry*	Country code defined in ISO 3166-1 alpha-2	2 letters text		Finland
	id*	Patient or aggregate identification number	Unique integer		12345678
	cohort*	Cohort name	Text		THL
	region*	Region name	Text		Pirkanmaa
	dataset*	Data set name	text		Elderly
	sex*	Sex	Numeric (Binary)	0=Female 1=Male	0
	dob* (alternatively age)	Date of birth or age at the start of the follow-up (children: months; adults:years)	dd/mm/yyyy	Date between the date of birth of the oldest and youngest study subject	01/01/1960

The follow-up	startdate*	Date of the start of the study period	dd/mm/yyyy	Date within the study period	30/12/2017
	enddate*	Date of the end of the study period ^a	dd/mm/yyyy	Date within the study period	30/12/2017
	middledate	Date separating the early and the middle epidemic season	dd/mm/yyyy	Date within the study period	30/12/2017
	latedate	Date separating the middle and the end epidemic season	dd/mm/yyyy	Date within the study period	30/12/2017
	death*	Died during the follow-up	Numeric (Binary)	0=No 1=Yes	1
	deathdate*	Date of death ^a	dd/mm/yyyy	Date within the study period	30/12/2017
	moved(*)	Moved out of the cohort catchment area during the follow-up	Numeric (Binary)	0=No 1=Yes	1

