Annex 3: Sample size considerations for cohort studies

Authors: [name] and [name]

For questions or feedback, please contact

e-mail: [contact]

This document provides sample size estimations for estimating overall and brand-specific influenza vaccine effectiveness (VE) using the cohort design. The minimal detectable VE as well as precision estimates are provided for various parameter settings and recommendations are formulated.

Minimal detectable vaccine effectiveness

The minimal detectable VE is the smallest VE that can be detected as significantly greater than zero in a given study using hypothesis testing. The minimal detectable VE for a cohort study is estimated as

$$VE_{MD} = 1 - RR_{MD(RR<1)}, \quad (1)$$

where $RR_{MD(RR<1)}$ is the minimal detectable relative risk (RR) if $RR < 1$, or

$$RR_{MD(RR<1)} \cong \frac{1}{2a} \left(b - \sqrt{b^2 - 4ac} \right), \quad (2)$$

where

$$a = Y + \pi Z; \quad b = 2Y + Z; \quad c = Y - r(1 - \pi)Z,$$

in which

$$Y = rN\pi^2; \quad Z = (r + 1)\pi \left(z_{\frac{\alpha}{2}} + z_{\beta} \right)^2$$

for attack rate in the unexposed π , exposed to unexposed ratio r with $r = \gamma/(1 - \gamma)$ with coverage γ , total sample size N , and where z_{α} and z_{β} are the standard normal z-score for the type I and type II error rates (Woodward 2013).

We calculated the minimal detectable overall VE (1) with 80% power ($1 - \beta$) and a two-sided 95% confidence coefficient ($1 - \alpha/2$) for cohort studies with the total number of subjects varying from 1000 to 50000, while assuming overall vaccination coverages of 5%, 20%, 50% and 70% and an attack rate of 5% and 15% in the unvaccinated.

We additionally calculated the minimal detectable brand-specific VE, where subjects are considered exposed when they were vaccinated with the brand of interest and unexposed when they were unvaccinated during the study's follow-up. This means that the same comparator group of unexposed subjects is used for the different brand-specific estimates. The minimal detectable brand-specific VE is calculated for the same settings above, additionally assuming that the brand of interest accounts for 10%, 20%, 40%, 60%, 80% and 90% of the overall vaccination coverage.

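### Region is collected in the minimum dataset but not named for adjustment, so in multi-region sites brand-specific VE can absorb regional differences in attack rate or testing

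*Combined protocol and SAP*

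**What the plan says.** - **Model.** Under Measure of effect, adjusted brand-specific, type-specific and overall estimates come from "regressing the health outcomes of interest on exposure status, age, sex and the confounders of interest". The last item is open-ended, and region is not named.
- **Guaranteed adjustment.** Under Potential confounders and effect modifiers: "The minimum set for a pooled analysis is marked with an asterisk". Only age and sex carry it. The list has no item for region or place of residence. Sites complete the rest: "Each study site to describe the factors included in the study & how these are identified".
- **Dataset.** Annex 1 asterisks region as a field separate from country and cohort, under General rather than among the confounders. Its introduction says "The minimum dataset is marked with an asterisk(*), but preferably the most important covariates to adjust for will be included".
- **Comparator.** Annex 3 states that "the same comparator group of unexposed subjects is used for the different brand-specific estimates".
- **Sites and brand choice.** Under Study sites: "Study sites may be local, regional or national". Under Study setting, each site describes "which vaccines are used in the database catchment area, and how the choice of vaccine brand happens". Nothing carries that description into the analysis.
- **Pooling.** "Information on the two-stage pooling of data from several study sites is provided in the DRIVE D4.4", so VE is estimated within each site and then combined.
- **Bias section.** Addressing confounding & bias covers frailty, care-seeking, misclassification and selection, but not geography. Its propensity score is for being vaccinated at all.
- **Pending.** Annex 2, the generic site-level SAP, has still to be developed.

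**The concern.** Brand-specific VE is the first-named part of the primary objective. Suppose a national register is one site and a brand is used mainly in some of its regions. The brand's recipients are then concentrated in those regions, while the unvaccinated comparator comes from all of them. If those regions had a larger epidemic, or tested more, the brand looks less effective than it is, and a brand used elsewhere looks better. The Outcome section says sampling usually follows local medical practice, so recorded attack rates could differ by region through testing alone.

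Age and sex do not carry this information. Two-stage pooling separates sites, not regions within a site. A propensity score for any vaccination need not pick up which brand a region uses. If coverage is equal across regions, overall VE stays correct, so the headline estimate gives no warning. A larger cohort only narrows the interval around the wrong value.

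**Working it through.** **1. The plan's own base case.** Annex 3, equation (3), with N = 5000, attack rate 5%, true VE 50% and two-sided 95% limits. At 50% coverage the cases are A1 = 5000 × 0.5 × 0.05 × 0.5 = 62.5 and A0 = 125, with N1 = N0 = 2500.

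SE = √(1/62.5 − 1/2500 + 1/125 − 1/2500) = √0.0232 = 0.152; lower limit = 1 − 0.5 × exp(1.96 × 0.152) = 32.6%.

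The same formula gives 24.7% at exactly 20% coverage and 25.3% at 21%, so the stated lower limit above 25% for coverage over 20% reproduces. The calculation uses one attack rate and one brand share for the whole cohort.

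**2. Regional assumptions (not in the documents).** Two regions of equal size, equal coverage, mean attack rate 5% in the unvaccinated, and true VE 50% for two brands with complementary shares. Let w be the fraction of a brand's recipients who live in region 1.

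**3. Expected VE without region in the model.**

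VE = 1 − 0.5 × [w × AR₁ + (1 − w) × AR₂] / [(AR₁ + AR₂)/2]

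| AR₁ / AR₂ | Brand split | Brand A | Brand B | Bias (points) |
|---|---|---|---|---|
| 5% / 5% | any | 50% | 50% | 0 |
| any | equal shares | 50% | 50% | 0 |
| 5.5% / 4.5% | 60/40 | 49% | 51% | 1 |
| 6% / 4% | 80/20 | 44% | 56% | 6 |
| 7% / 3% | 80/20 | 38% | 62% | 12 |
| 6% / 4% | one brand per region | 40% | 60% | 10 |
| 7% / 3% | one brand per region | 30% | 70% | 20 |

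Example, 7%/3% with 80/20, brand A: 0.8 × 7 + 0.2 × 3 = 6.2; 0.5 × 6.2/5 = 0.62; VE 38%. Overall VE is 50% in every row.

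**4. With region as a stratum.** In each region the brand's risk is 0.5 × AR and the comparator's is AR, so the RR is 0.5 and VE is 50% for both brands.

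**5. Precision cost.** N = 5000, 50% coverage, the variance in equation (3), inverse-variance weighting over regions. Take 7%/3%, one brand per region, and the brand in the 3% region: N1 = 1250, A1 = 1250 × 0.03 × 0.5 = 18.75.

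- Unstratified (N0 = 2500, A0 = 125): variance = 1/18.75 − 1/1250 + 1/125 − 1/2500 = 0.0601. Placed around the true 50%, the lower limit is 19.1%.
- Stratified (N0 = 1250, A0 = 37.5): variance = 1/18.75 − 1/1250 + 1/37.5 − 1/1250 = 0.0784, which is 30% larger. The lower limit is 13.4%.

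For one brand per region the increases are 10% and 30% at 7%/3%, and 15% and 25% at 6%/4%. With an 80/20 split they are about 4% to 7%.

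The 19.1% is not what an unstratified analysis would report in that scenario. Its estimate is 70%, with interval 1 − 0.30 × exp(±1.96 × √0.0601), or 51.5% to 81.4%, which excludes the true 50%.

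**The case against.** A reader might infer that region is excluded from the models and that brand VE is therefore confounded wherever brand supply differs by region. The documents support neither step.

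- **Not excluded.** The model has an open confounder term, sites may add factors, Annex 1 foresees covariates for adjustment or stratification, and Annex 2 and the site SAPs are to settle the details. This is an adjustment not yet specified. That stands. It does not remove the point, because only the asterisked set is guaranteed for pooling and region is outside it.
- **Two conditions, not one.** Supply differences alone cause no bias: attack rate or testing must also differ between regions of the same site. No section reports regional attack rates or says that brand supply varies within any site. That stands.
- **Limited scope.** Two-stage pooling keeps between-site differences out of the site estimates, so single-region sites are unaffected. That stands.
- **Size.** Every regional input is assumed, and mild ones give about 1 point. That stands, so a range starting at zero is the honest statement.
- **Cost.** Stratifying is not free for a geographically concentrated brand. That stands too, but it does not argue against adjustment: the tighter unstratified interval is centred on a biased value.

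**Conclusion.** The point holds in a limited form. Region is collected from every site, is missing from the confounder list and the guaranteed adjustment set, and is not named in the model. A multi-region site that followed the stated minimum could therefore report biased brand-specific VE, and the same reasoning applies to type-specific VE. Whether it would do so depends on brand share and attack rate (or testing) both varying between its regions, which the documents do not show.

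Under two equal regions, equal coverage and true VE 50%, the bias runs from zero, through 1, 6 and 12 points, to 20 points in the most extreme case examined. In that last case two equally effective brands would show 30% and 70%. These are illustrations, not predictions for any site. The change is worth making before Annex 2 is written.

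**What to change.** 1. In Potential confounders and effect modifiers, add region with an asterisk, so that it joins age and sex in the minimum adjustment set.
2. In Measure of effect and Annex 2, state that brand- and type-specific models in sites covering more than one region are stratified by region (Cox) or include region terms (Poisson, logistic). Recipients are then compared with unvaccinated people of the same region.
3. Have each multi-region site report brand share by region, next to its description of how brand is chosen.

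The change needs no new data, since region is already in the minimum dataset. The precision loss is small in most settings (about 4% to 7% of variance with an 80/20 split) but about 10% to 30% for a brand confined to one region, so sample size statements for such a brand should allow for it.
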